## CONCLUSION

The hazards/risks associated with iDesign 1.3-PRESBY TPS using the iDesign Advanced WaveScan Studio System in conjunction with the STAR S4 IR Excimer laser are acceptable and expected to be similar to those of LASIK treatment using the iDesign System and STAR S4 IR Excimer laser. The potential clinical benefits of treatment using the iDesign Advanced WaveScan Studio System in conjunction with the STAR S4 IR Excimer laser outweigh the residual risks when the device is used as intended.

## **18. RECORDS RETENTION**

All study-related correspondence, subject records, consent forms, Authorization for Use/Disclosure of Health Information Forms or similar medical treatment privacy law documentation, records of the distribution and use of all study products, and original case report forms should be maintained by the investigator.

The investigator must maintain and have access to the following essential documents until notified by the Sponsor. Note: This may be for a minimum of 15 years after completion of the study unless country-specific requirements are longer. AMO requires notification if the investigator wishes to relinquish ownership of the data so that mutually agreed-upon arrangements can be made for transfer of ownership to a suitably qualified, responsible person.

- All case report forms
- All adverse event information (adverse event forms, follow-up letters, etc.)
- Investigational supply records/inventory
- IRB and regulatory approval documentation
- Study correspondence
- Study agreements
- Site visit documentation
- Protocol(s) and the reason for any deviations from the protocol
- Subject log(s)
- Clinical Investigator's Brochure
- Completed subject informed consent forms and medical privacy forms (e.g., Authorization for Use/Disclosure of Health information or equivalent documentation necessary to comply with applicable privacy laws pertaining to medical treatment in the governing countries)
- Subject medical chart/clinic notes

## **19. TERMINATION OF THE INVESTIGATION**

The clinical investigation will be suspended in the event of high levels of complications and/or adverse events that are unexpected in nature and/or severity and evaluated as to causality relative to the study device. The clinical investigation may be suspended if the Medical Monitor or IRB, upon review and evaluation of the clinical data, finds unacceptable clinical performance or the level of single or total complications and/or adverse events unacceptable for continuation of the investigation.

If causality is shown not to be related to the study device, the study may be resumed in accordance with the IRB and regulations of Health Canada and governing countries. The study will be terminated if causality is shown to be related to the study device.

Additionally, the investigator, or AMO, may stop a subject's participation at any time. AMO may also stop the study at any time for reasons it determines appropriate. However, no suspension of the study would be made to disadvantage the study subjects. Following suspension of the study for any reason, all study subjects who have already received treatment would continue to be followed through completion of the study visit schedule.

## **20. STATISTICAL METHODS**

This section highlights the analyses for the primary and secondary study endpoints as well as the key safety endpoints. The key time point for analyzing study endpoints will be at 6 months.

### **20.1 ANALYSIS POPULATION**

The safety population will be the primary analysis population for all endpoints and includes all eyes that receive study treatment.

### **20.2 PRIMARY AND SECONDARY STUDY ENDPOINTS**

#### **Primary Endpoint**

##### **MONOCULAR DISTANCE CORRECTED INTERMEDIATE VISUAL ACUITY (DCIVA)**

The primary endpoint is mean monocular DCIVA under photopic conditions at 67 cm. Results will be reported by PresbyT-LASIK treatments (test) group versus iDesign CustomVue (control) group and compared using a one-sided, paired t-test with alpha level of 0.025. The null hypothesis is that the mean difference between eyes (control minus test) for LogMAR DCIVA is less than or equal to zero (ie, test acuity is the same as or worse than that of control). The alternative hypothesis is that the mean difference between eyes for DCIVA is greater than zero (ie, test acuity is better than that of control).

$H_0: \mu_{\text{diff}} \leq 0$  (test is worse than (higher LogMAR) or equal to control)

$H_1: \mu_{\text{diff}} > 0$  (test is better (lower LogMAR) than control)

where

$\mu_{\text{diff}}$  = the mean difference in LogMAR DCIVA between control eyes and test eyes (control minus test)

Reject the null hypothesis if one-sided p-value  $\leq 0.025$ .

The success criterion is a statistically significantly lower mean DCIVA for test compared to control ( $p \leq 0.025$ ).

In addition, clinical significance will be achieved if the mean DCIVA for the test group is at least one line better than that for the control group.

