## **4. STUDY DESIGN**

This study is a 9 month, prospective, multicenter, non-randomized, contralateral, open-label clinical study.

The study will be conducted at up to 4 sites in Canada and will include up to 34 test group treated eyes (of up to 34 subjects). Subjects must have both eyes treated in the study. The dominant eye will be treated with the control product; the non-dominant eye will be treated with test product. Analyses will be conducted at 6 months.

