## **Secondary Endpoints**

### MONOCULAR DISTANCE CORRECTED NEAR VISUAL ACUITY (DCNVA)

Mean monocular DCNVA at 40 cm will be reported by PresbyT-LASIK treatments (test) group versus iDesign CustomVue treatments (control) group and compared using a one-sided, paired t-test with an alpha level of 0.025. The null hypothesis is that the mean difference between eyes (control minus test) for logMAR DCNVA is less than or equal to zero. The alternative hypothesis is that the mean difference between eyes for DCNVA is greater than zero.

$H_0: \mu_{\text{diff}} \leq 0$  (test is worse than (higher logMAR) or equal to control)

$H_1: \mu_{\text{diff}} > 0$  (test is better (lower logMAR) than control)

where

$\mu_{\text{diff}}$  = the mean difference in logMAR DCNVA between control eyes and test eyes (control minus test)

Reject the null hypothesis if one-sided p-value  $\leq 0.025$ .

The success criterion is a statistically significantly lower mean logMAR value for test compared to control eyes ( $p \leq 0.025$ ).

Clinical significance is achieved if the mean DCNVA for the test group is at least 1.5 lines better than that for the control group.

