## APPENDIX A SUMMARY OF PROCEDURES REQUIRED AT EACH VISIT

Examination	Preop Days -120 to -21 	CL Disp Weeks -3 	CL F/U Weeks -2 	Op Day 0	1 Day Days 1-2	1 Wk Days 5-9	1 Mo Weeks 3-5	3 Mo Weeks 10-14	6 Mo Weeks 21-26	9 Mo Weeks 35-43	Unsched 
Informed consent	X										
Ocular and systemic medical history and concomitant medications	X			X	X	X	X	X	X	X	
Inclusion/Exclusion criteria	X										
PRO questionnaire - PRVSQ	X						X	X	X	X	X 
iDesign System Measurement of refraction, aberrometry, topography, keratometry, pupilometry	X					X	X	X	X	X	X (after 1 week)
UCDVA - photopic, monocular, distance (logMAR)	X				X	X	X	X	X	X	X (after 1 week)
UCDVA - photopic, binocular, distance (logMAR)								X	X	X	
Manifest refraction (logMAR)	X					X	X	X	X	X	X
BSCVA - photopic, monocular, distance (logMAR)	X					X	X	X 	X 	X 	X 
BSCVA - photopic, binocular, distance (logMAR)								X	X	X	
BSCVA - photopic, monocular, distance low contrast (10%) (logMAR)	X							X	X	X	
DCNVA - mesopic, monocular at 40 cm (logMAR)								X	X	X	
Pupil size, mesopic, distance & near								X			
Pupil size, photopic, distance & near								X			
Minimum add power	X										
DCIVA - photopic, monocular at 67 cm (logMAR)	X							X	X	X	
DCIVA - photopic, binocular at 67 cm (logMAR)	X							X	X	X	
DCNVA - photopic, monocular at 40 cm (logMAR)	X							X	X	X	
DCNVA - photopic, binocular at 40 cm (logMAR)	X							X	X	X	
UCIVA - photopic, monocular at 67 cm (logMAR)								X	X	X	
UCIVA - photopic, binocular at 67 cm (logMAR)								X	X	X	
UCNVA - photopic, monocular at 40 cm (logMAR)								X	X	X	
UCNVA - photopic, binocular at 40 cm (logMAR)								X	X	X	
Defocus curve testing – photopic, monocular (logMAR)								X	X	X	
Keratometry (auto or manual)	X					X	X	X	X	X	X 
Corneal topography	X						X	X	X	X	X 
Anterior segment exam (biomicroscopic slit-lamp exam  )	X				X	X	X	X	X	X	X
Intraocular pressure (applanation tonometry)	X						X	X	X	X	X 
Pachymetry	X								X		
Cycloplegic refraction	X								X		X 
Dilated fundus exam	X								X		X 
Complications	X	X	X	X	X	X	X	X	X	X	X

Examination	Preop Days -120 to -21 	CL Disp Weeks -3 	CL F/U Weeks -2 	Op Day 0	1 Day Days 1-2	1 Wk Days 5-9	1 Mo Weeks 3-5	3 Mo Weeks 10-14	6 Mo Weeks 21-26	9 Mo Weeks 35-43	Unsched 

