## APPENDIX N      CLINICAL WORKFLOW & LASIK SURGICAL PROCEDURE

### Clinical Workflow:

1. Patients will be measured on the iDesign 1.2 system.
2. The same iDesign system will be used for all measurements (in the event there is more than one iDesign in the center).
3. Preoperatively, iDesign exams will be acquired until an exam is selected for treatment. Postoperatively, a single iDesign exam will be acquired.
4. The iDesign 1.2 system database will be exported using the iDesign Export functionality on the Utilities Tab for all exams of the patient(s) being treated.
5. The exported patient database will be imported into the iDesign 1.3-PRESBY software (modified for this study) on the AMO provided laptop.
6. The treatments for the control and test eyes will be programmed and designed on the iDesign 1.3 PRESBY software. No Physician Adjustment or Percentage Nomogram adjustments will be used.
7. The treatments for the test eye (non-dominant eye) with presbyopia option turned **ON** and the control eye (dominant eye) with presbyopia option turned **OFF** will be calculated on iDesign 1.3-PRESBY software for the selected exams.
8. Treatments will be saved to USB and transferred to the STAR S4 IR laser.
9. Treatments will be executed on the STAR S4 IR laser.

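### Eyes are allocated by dominance, yet the DCIVA and DCNVA tests ignore the preoperative monocular values already collected in each eye

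*Protocol*

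**What the plan says.** **Allocation.** Protocol section 4 fixes treatment by dominance: "The dominant eye will be treated with the control product; the non-dominant eye will be treated with test product". The Clinical Workflow in Appendix N repeats this; it has "The treatments for the test eye (non-dominant eye) with presbyopia option turned" on, and off for the dominant eye. The design is declared non-randomised and open-label, and the Synopsis says that subjects and vision testers are unmasked.

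**Tests.** In Protocol 20.2 and SAP 3.3, DCIVA for test and control is "compared using a one-sided, paired t-test with alpha level of 0.025". For DCNVA (Protocol 20.2, SAP 3.4) it is "compared using a one-sided, paired t-test with an alpha level of 0.025". In both, the variable is the control-minus-test difference in logMAR, evaluated at 6 months, with no preoperative term. Protocol 20.2 says of the primary endpoint: "The success criterion is a statistically significantly lower mean DCIVA for test compared to control". A separate sentence adds that "clinical significance will be achieved if the mean DCIVA for the test group is at least one line better".

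**Preoperative data.** In Protocol Appendix A the rows "DCIVA - photopic, monocular at 67 cm (logMAR" and "DCNVA - photopic, monocular at 40 cm (logMAR" are both marked in the preoperative column. The plan does use preoperative values for BSCVA, which is analysed as postoperative minus preoperative (Protocol 20.2, SAP 3.5).

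**Tables.** SAP Appendix I lists only refractions under preoperative characteristics. Its DCIVA and DCNVA rows name no visit. SAP 3.6 reports DCIVA and DCNVA by group with mean differences, also without naming the preoperative visit.

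**The concern.** Treatment and dominance are completely confounded. Pairing removes what a subject's two eyes share. It cannot remove a consistent difference between dominant and non-dominant eyes, and without randomisation nothing makes that difference zero on average.

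If the non-dominant eye already had slightly better intermediate or near acuity through its distance correction, and this lasted to 6 months, the planned test would count it as treatment effect. If the non-dominant eye started slightly worse, a real effect would be harder to detect. The preoperative measurements are the direct evidence on this point. As written, they enter neither efficacy test, and nothing in the table list ensures that a reader will see them by eye group.

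**Working it through.** **Inputs from the plan** (Protocol 20.6, SAP 4): n = 34, difference 0.7 line, SD 1.4 lines, two-sided alpha 0.05, equivalent here to one-sided 0.025. The plan does not say what the SD refers to. It is read as the SD of the between-eye difference, because that reading reproduces the stated power.

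**Assumptions not in the plan:** a preoperative offset b in lines (control minus test; positive favours the test eye) that persists in full to 6 months; the correlation r between the preoperative and 6-month between-eye differences; and k, the ratio of the preoperative SD to the 6-month SD of those differences.

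**1. The plan's own figure.** Noncentrality = (0.7/1.4) × √34 = 2.915 with 33 df. Power is 80.8%, which agrees with the stated figure of over 80%.

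**2. Smallest significant mean.** SE = 1.4/√34 = 0.240 line. Multiplying by the 0.975 quantile of t with 33 df gives 0.488 line.

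**3. Planned test with a persisting offset.** Noncentral t, 33 df. Error uses a true mean of b; power uses 0.7 − b when the offset is against the test eye. The last column is the normal probability that the observed mean is at least one line when the offset is the only effect, for example (1 − 0.3)/0.240 = 2.92 SEs.

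| Offset (lines) | Error, favours test eye | Power at 0.7, against test eye | P(mean ≥ 1 line), offset only |
|---|---|---|---|
| 0 | 2.5% | 80.8% | – |
| 0.1 | 6.0% | 67.9% | 0.0001 |
| 0.2 | 12.5% | 52.5% | 0.0004 |
| 0.3 | 22.8% | 36.6% | 0.0018 |

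**4. Regression adjustment.** The 6-month difference is regressed on the uncentred preoperative difference and the intercept is tested (32 df; 200,000 simulated trials per cell). The expected slope is r/k, so the offset left in the intercept is b × (1 − r/k). For example, b = 0.2, r = 0.5, k = 1 leaves 0.2 × 0.5 = 0.1 line.

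With no offset, error is 2.5 to 2.6%. Power at 0.7 line is 79.6% at r = 0, about 83% at r = 0.3, about 89% at r = 0.5 and about 93.5% at r = 0.6, and hardly depends on k.

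Error with an offset favouring the test eye, at r = 0.3 / 0.5 / 0.6:

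| Offset | k = 0.5 | k = 1 | k = 1.5 |
|---|---|---|---|
| 0.1 | 3.6 / 2.5 / 2.0% | 4.7 / 4.2 / 3.9% | 5.2 / 4.9 / 4.8% |
| 0.2 | 5.0 / 2.5 / 1.6% | 8.3 / 6.6 / 5.8% | 9.7 / 8.9 / 8.7% |
| 0.3 | 6.7 / 2.6 / 1.3% | 13.6 / 10.0 / 8.5% | 16.7 / 14.6 / 14.3% |

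At r = 0 the bias is not reduced: error at 0.2 line is 11.7 to 12.1%, below 12.5% only because the intercept has a wider SE.

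**5. Change score** (between-eye difference in change from preoperative). Its SD is 1.4 × √(1 + k² − 2rk). Error stays at 2.4 to 2.6% for every offset. Power at 0.7 line for r = 0 / 0.3 / 0.5 / 0.6 is:

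- k = 0.5: 71.7 / 82.8 / 90.5 / 94.0%
- k = 1: 51.7 / 66.6 / 80.8 / 88.5%
- k = 1.5: 35.0 / 45.6 / 57.3 / 65.4%

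The SD falls below 1.4 only if r > k/2, so only then does the change score have more power than the planned test.

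The plan gives no SD for near acuity, so none of these figures is specific to DCNVA.

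**The case against.** **No offset is shown.** This stands. Its existence, size, direction and full persistence are all assumed. The acuity and add-power criteria apply to each eye (Protocol 8.1), and DCIVA and DCNVA are tested through the distance correction (Appendix F), so a large offset is unlikely. These requirements do not, however, equalise intermediate or near acuity between eyes to within a fraction of a line.

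**The one-line threshold protects the result.** Protocol 6.1 puts statistical and clinical significance under one success heading. If both were required, an offset alone would succeed with probability of at most about 0.002, well under 2.5%. This limits the harm considerably. But Protocol 20.2 and SAP 3.3 attach success to p ≤ 0.025 and state clinical significance separately, and that p-value can be reached with an observed mean of 0.49 line.

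**The regression does not cure the defect.** This is largely right. In most settings above it leaves part of the offset, and where r exceeds k it over-corrects. Only the change score restores 2.5%, and it can cost much power. The documents give neither r nor k, so the choice of primary model is a judgement; this is why all three analyses should be reported.

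**The tables may already cover it.** SAP 3.6 and Appendix I do not exclude a preoperative column. They do not require one either.

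**It is an openly non-randomised feasibility study.** True, but it has a powered hypothesis test with a success rule, and the plan already uses preoperative values for BSCVA.

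**Conclusion.** The concern holds. Allocation follows dominance, both efficacy tests use unadjusted 6-month between-eye differences, and the preoperative values that bear on the resulting confounding are collected but not used in those tests or explicitly tabulated by eye group.

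Under the assumed offsets of 0.1 to 0.3 line, the DCIVA test's error could be 6.0 to 22.8% rather than 2.5%, or its power 67.9 to 36.6% rather than 80.8%. These figures show sensitivity; they are not evidence of bias. They rest on 1.4 lines being the SD of the paired difference and on full persistence of the offset. The point concerns how far the p-value can be interpreted; a false finding of a one-line benefit from an offset alone is very unlikely. It should be addressed, because the data are already collected.

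**What to change.** In the SAP, and correspondingly in Protocol 20.2:

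1. For DCIVA, and likewise DCNVA, make the primary test a regression of the 6-month control-minus-test difference on the same subject's preoperative control-minus-test difference. Leave the covariate uncentred and test the intercept one-sided at 0.025. Centring would make the intercept the raw mean difference again.
2. Keep two sensitivity analyses: the unadjusted paired t-test, and the between-eye difference in change from preoperative.
3. Add to SAP Appendix I a table of preoperative monocular DCIVA and DCNVA by eye group, with the mean between-eye difference.
4. State as limitations that adjustment may remove only part of a persisting offset, and that other effects of dominance and unmasked testing remain.

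Settle this before postoperative DCIVA and DCNVA are compared between eyes; Protocol 20.5 already schedules periodic analyses of them from the 3-month visit.

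The cost is SAP wording, one model per endpoint and one table, with no new visits or measurements. The model uses one degree of freedom. If r = 0, power at 0.7 line falls from 80.8% to 79.6%, about 1.2 points; at r = 0.5 it rises to about 89%.

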## **Secondary Endpoints**

### MONOCULAR DISTANCE CORRECTED NEAR VISUAL ACUITY (DCNVA)

Mean monocular DCNVA at 40 cm will be reported by PresbyT-LASIK treatments (test) group versus iDesign CustomVue treatments (control) group and compared using a one-sided, paired t-test with an alpha level of 0.025. The null hypothesis is that the mean difference between eyes (control minus test) for logMAR DCNVA is less than or equal to zero. The alternative hypothesis is that the mean difference between eyes for DCNVA is greater than zero.

$H_0: \mu_{\text{diff}} \leq 0$  (test is worse than (higher logMAR) or equal to control)

$H_1: \mu_{\text{diff}} > 0$  (test is better (lower logMAR) than control)

where

$\mu_{\text{diff}}$  = the mean difference in logMAR DCNVA between control eyes and test eyes (control minus test)

Reject the null hypothesis if one-sided p-value  $\leq 0.025$ .

The success criterion is a statistically significantly lower mean logMAR value for test compared to control eyes ( $p \leq 0.025$ ).

Clinical significance is achieved if the mean DCNVA for the test group is at least 1.5 lines better than that for the control group.

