#### **20.5 PERIODIC REPORTS**

Periodic analyses of data from all eyes completing the 3-month and 6-month visits to evaluate UCDVA, MRSE, BSCVA, DCIVA, DCNVA and safety outcomes including biomicroscopic findings and adverse events will be conducted.

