3.4 SECONDARY ENDPOINT

MONOCULAR DISTANCE CORRECTED NEAR VISUAL ACUITY (DCNVA)

Mean monocular DCNVA at 40 cm will be reported by CustomVue combined with iDesign 1.3-PRESBY treatments (test) group versus CustomVue treatments (control) group and compared using a one-sided, paired t-test with an alpha level of 0.025. The null hypothesis is that the mean difference between eyes (control minus test) for logMAR DCNVA is less than or equal to zero. The alternative hypothesis is that the mean difference between eyes for DCNVA is greater than zero.

 $H_o: \mu_{diff} \leq 0$ (test is worse than (higher logMAR) or equal to control)

H₁: $\mu_{diff} > 0$ (test is better (lower logMAR) than control)

where

 μ_{diff} = the mean difference in logMAR DCNVA between control eyes and test eyes (control minus test)

Reject the null hypothesis if one-sided p-value ≤ 0.025 .

The success criterion is a statistically significantly lower mean logMAR value for test compared to control eyes ($p \le 0.025$).

Clinical significance is achieved if the mean DCNVA for the test group is at least 1.5 lines better than that for the control group.

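### DCIVA and DCNVA each carry their own success claim at one-sided 0.025, and neither document makes the DCNVA claim depend on DCIVA

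*Protocol*

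**What the plan says.** For DCIVA at 67 cm, protocol 20.2 specifies a "one-sided, paired t-test with alpha level of 0.025" and then: "The success criterion is a statistically significantly lower mean DCIVA for test compared to control". For DCNVA at 40 cm it specifies a "one-sided, paired t-test with an alpha level of 0.025" and then: "The success criterion is a statistically significantly lower mean logMAR value for test compared to control eyes". SAP 3.3 and 3.4 repeat both; in SAP 3.4 the near-acuity groups are again "compared using a one-sided, paired t-test with an alpha level of 0.025".

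Each endpoint also has its own clinical-significance threshold: one line for DCIVA and 1.5 lines for DCNVA. The documents label DCIVA primary and DCNVA secondary and evaluate both at 6 months (protocol 6 and 20, SAP 1). SAP 2.3 sets a default two-sided alpha of 0.05. Neither document states a testing order, an alpha split or any other multiplicity rule.

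**The concern.** A success criterion says what the sponsor may conclude. Here there are two, each met by its own p-value alone. If DCIVA misses and DCNVA reaches p ≤ 0.025, the text as written supports declaring success on DCNVA, and nothing says what standing that result has. The outcome is not far-fetched: the clinical hypothesis (protocol 1 and 3) puts intermediate and near acuity side by side as what the study is to show.

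With two separate chances to succeed, a treatment with no effect on either endpoint produces at least one false success more often than either test does alone.

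**Working it through.** **Inputs**
- Level of each test: one-sided 0.025 (protocol 20.2; SAP 3.3, 3.4).
- Sample size basis: 34 subjects, difference 0.7 line, SD 1.4 lines, two-sided alpha 0.05, paired t-test (protocol 20.6; SAP 4).
- Correlation between the DCIVA and DCNVA paired differences: not given. Assumed range 0 to 0.9.

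**Step 1. The plan's own figure.** The noncentrality is (0.7/1.4) × √34 = 2.915 on 33 degrees of freedom. The noncentral t gives power 80.8%, whether the test is two-sided at 0.05 or one-sided at 0.025. With 33 subjects it is 79.5%. The stated power of over 80% with 34 subjects is reproduced.

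**Step 2. Error across the two claims, no order.** With both nulls true at zero difference,

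P(at least one false success) = 1 − P(Z₁ < 1.96, Z₂ < 1.96).

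For correlation 0 this is 1 − 0.975² = 1 − 0.950625 = 4.94%. For other correlations it comes from the bivariate normal. DCIVA alone contributes 2.5%. The remainder is the chance of a false DCNVA success when DCIVA has not been rejected.

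| Assumed correlation | At least one false success | Of which DCNVA only, after DCIVA fails |
|---|---|---|
| 0 | 4.94% | 4.94 − 2.50 = 2.44% |
| 0.5 | 4.54% | 4.54 − 2.50 = 2.04% |
| 0.8 | 3.90% | 3.90 − 2.50 = 1.40% |
| 0.9 | 3.52% | 3.52 − 2.50 = 1.02% |

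The upper bound, whatever the correlation, is 0.025 + 0.025 = 5.0%. Simulated paired t-tests with 34 pairs (100,000 null trials per scenario, two scenarios per correlation) agree: 4.8% to 5.0% at correlation 0, about 4.5% to 4.6% at 0.5, and 3.8% to 3.9% at 0.8.

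**Step 3. With DCIVA tested first.**
- If the DCIVA null is true, any false claim requires rejecting it, which has probability at most 2.5%.
- If the DCIVA null is false, the only possible false claim is DCNVA, which is still tested at 2.5%.

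The family-wise error is therefore at most 2.5% in every case. The DCIVA test is unchanged, so its power stays at 80.8% with 34 subjects.

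**Step 4. The alternative.** Splitting alpha as 0.0125 one-sided each also holds 2.5%, but DCIVA power with 34 subjects falls to 71.3%.

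**The case against.** The case for leaving the text alone is fair. The plan sets 0.025 for each test and never claims 2.5% across both, and the primary test alone does keep 2.5%. The labels already rank the endpoints, the sample size rests on DCIVA only, and no study-level rule lets DCNVA replace DCIVA. This is a feasibility study, non-randomized and open-label, where strict control over one secondary endpoint is less pressing than in a confirmatory trial. All of this stands, and it limits the consequence. It does not supply the missing rule: a label states importance, not a condition for testing, and both documents chose formal hypotheses and success criteria for DCNVA.

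A reader might go further and infer from protocol 20.5 that the plan adds unadjusted interim looks, since it foresees "Periodic analyses of data from all eyes completing the 3-month and 6-month visits to evaluate UCDVA, MRSE, BSCVA, DCIVA, DCNVA" together with safety outcomes, and the SAP does not describe these reports. The documents do not support that reading. Section 20.5 names no hypothesis test, alpha, success claim or stopping rule. Success is tied to 6 months, and the 6-month periodic analysis may simply be the main analysis.

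Nor does the sponsor's general right to stop (protocol 19) amount to an efficacy stop. No favourable result is tied to it, and treated subjects stay in follow-up after a suspension. The number to be treated is worded in several ways, but no section lets periodic results set it. Any inflation figure for repeated looks would rest on a schedule that neither document contains.

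**Conclusion.** The point holds for the missing testing order only. As written, DCNVA success can be declared after the primary has failed, and the chance of at least one false efficacy success is about 3.5% to 4.9% over assumed correlations from 0.9 down to 0. These figures assume that neither endpoint has a true effect and that each 6-month test is run once. They do not show that either test exceeds its own 2.5%, or that the plan breaks a family-wise promise, because it makes none. The practical matter is what may be concluded from a positive DCNVA after a negative DCIVA. The consequence is modest, but the remedy costs almost nothing and is worth making.

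**What to change.** Add to protocol 20.2 (Secondary Endpoints) and SAP 3.4: *DCNVA is tested for success at one-sided 0.025 only if the DCIVA null hypothesis is rejected; otherwise DCNVA is reported descriptively.*

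This needs no extra subjects or data. The one downside is that DCNVA cannot be claimed as a success when DCIVA misses, even if its p-value is small; its estimate and confidence interval can still be reported.

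Optional clarification, separate from the error calculation: state in protocol 20.5 and in the SAP that the periodic reports are descriptive, and that the 6-month DCIVA and DCNVA tests are run once, on complete data.
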